2. TRIAL OBJECTIVES AND ENDPOINTS

2.1 MAIN OBJECTIVES, PRIMARY AND SECONDARY ENDPOINTS

2.1.1 Main objectives

The primary objective of this phase III pivotal trial in CIAS is to assess the efficacy in improving cognitive impairment using MCCB in patients with schizophrenia treated for 26 weeks with Iclepertin 10mg as compared with placebo.

The key secondary objective is to assess the efficacy in daily functioning of 26-week treatment with Iclepertin 10mg as compared with placebo in terms of Schizophrenia Cognition Rating Scale (SCoRS) and Virtual Reality Functional Capacity Assessment Tool (VRFCAT).

The secondary objectives are to assess the efficacy in improving reasoning and problem solving and patients' experience of cognitive impairment associated with their disease.

Patients will be required to be on stable antipsychotic treatment at the time of inclusion.

The primary treatment effect of interest is defined in the primary estimand framework as specified in detail in Section 7. All efforts will be taken to continue to collect efficacy data at planned visits after patients discontinued trial treatment following an intercurrent event. For patients who discontinued trial treatment after intercurrent events that will be handled by the treatment policy approach, these observed off-treatment data will be included in the primary analysis. For patients who discontinued trial treatment after other intercurrent events that will not be handled by the treatment policy approach, these observed off-treatment data will be censored and excluded from the primary analysis.

In summary, the primary treatment effect of interest is the effect obtained at the primary time point if patients had stayed on the treatment, i.e. taking the trial medication for the full treatment duration while allowing the following intercurrent events: change in concomitant medications or background non-pharmacological therapy, change in study partner, and treatment interruption or discontinuation due to exacerbation, an acute episode, adverse events (AEs) that are considered drug related and protocol-defined drug withdrawal.

2.1.2 Primary endpoint(s)

The primary efficacy endpoint is assessing cognition:

• Change from baseline in overall composite T-score of the MCCB after 26 weeks of treatment.

2.1.3 Secondary endpoint(s)

The key secondary efficacy endpoints are:

- Change from baseline in the SCoRS interviewer total score after 26 weeks of treatment
- Change from baseline to Week 26 in the adjusted total time T-score in the VRFCAT

[figure not shown]
c33087946-03

Page 30 of 112

[figure not shown]
Proprietary confidential information © 2023 Boehringer Ingelheim International GmbH or one or more of its affiliated companies

The secondary efficacy endpoints are as follows:

- Change from baseline to Week 26 in the T-score of the number of correct responses on ToL.
- Change from screening visit 1a to Week 24 in Patient Reported Experience of Cognitive Impairment in Schizophrenia (PRECIS) total score

3087946-03 Clinical Trial Protocol Page 31 of 112
Proprietary confidential information © 2023 Boehringer Ingelheim International GmbH or one or more of its affiliated companies

Page 32 of 112

Proprietary confidential information © 2023 Boehringer Ingelheim International GmbH or one or more of its affiliated companies

3. DESCRIPTION OF DESIGN AND TRIAL POPULATION

3.1 OVERALL TRIAL DESIGN

The overall trial design is as follows:

[figure not shown]

Figure 3.1:1 Trial design

This is a 26-week, multi-center, multi-national, randomized, double-blind, placebo controlled, parallel group trial in patients with schizophrenia. In total, approximately 586 patients with schizophrenia on stable antipsychotic treatment who meet the eligibility criteria are planned to be randomized in equal ratio into this trial.

Patients are enrolled in the trial once informed consent has been signed.

Patients who are deemed eligible by the investigator, after screening, will be randomized to the 26-week treatment period assigned with equal ratio to one of the following arms:

- Iclepertin 10 mg once daily
- Placebo once daily

Randomization of patients will be stratified by MCCB overall composite T-score at screening (screening MCCB overall composite T-score $<30, \ge 30$) via Interactive Response Technology (IRT) to balance the baseline cognitive level among groups.

Patients who finish 26 weeks of treatment with Iclepertin or placebo and the 4 week safety follow-up period in this study will be offered the opportunity for treatment with Iclepertin 10 mg in a long-term safety extension study. Patients may enter the extension trial after completing follow-up visit 6. For further details please refer to Section 6.2.4.

As part of this research program, optional biobanking and optional speech sample collection will be done in order to address future scientific questions as described in Section 5.5 and 5.6.1.

Page 33 of 112

Proprietary confidential information © 2023 Boehringer Ingelheim International GmbH or one or more of its affiliated companies

3.2 DISCUSSION OF TRIAL DESIGN, INCLUDING THE CHOICE OF CONTROL GROUP(S)

A parallel group design is appropriate to detect the effects of Iclepertin 10 mg compared to placebo on cognitive impairment in clinically stable patients with schizophrenia. The primary analysis of efficacy is planned after 26 weeks of treatment. Elimination of Iclepertin takes approximately 12 days, therefore 28 days is considered sufficient to detect any unexpected late onset AEs, to evaluate the pharmacodynamic effect of Iclepertin after discontinuation and to allow for assessment of reversibility of any unexpected side-effects. Refer to section 5.2.6.4 for follow up of Hb related issues.

Details of the statistical approach and sample size justification are given in Section 7.

There is currently no approved medication indicated for treatment of CIAS and therefore, a placebo control group is being used in this study. It should be noted that all patients, including those randomized to the placebo group, are permitted to remain on other antipsychotic and psychotropic medications, within the eligibility criteria. The risk to the control group is discussed in Table 1.4.2:1.

A DMC, independent from the Sponsor, will be established to review the safety data at regular intervals, and to recommend to the Sponsor whether to continue, modify, or stop the trial based on periodic safety monitoring. The tasks and responsibilities of the DMC members will be detailed in the DMC charter.

3.3 SELECTION OF TRIAL POPULATION

It is planned that approximately 100 trial centres in multiple countries will be participating in this trial and a sufficient number of patients will be screened for the trial to ensure that approximately 586 patients are randomized to trial treatment.

This is a global trial and patients from all ethnic and racial backgrounds may be included.

It is expected that approximately five patients will be randomized at each trial center. If enrolment is delayed, additional sites may be recruited. Sites that do not screen patients over a prolonged period of time may be closed.

Permission to randomize more than 30 patients per site must be obtained from the Clinical Trial Leader (CTL). This will only be allowed after a careful review of the enrolment status of the site.

Screening of patients for this trial is competitive. Investigators will be notified about screening completion and will then not be allowed to screen additional patients for this trial.

A log of all patients enrolled into the trial (i.e. who have signed informed consent) will be maintained in the ISF irrespective of whether they have been treated with investigational drug or not.

If a patient is entered (randomized) in error (does not meet all inclusion criteria or meets one or more exclusion criteria on the day of enrolment), the sponsor should be contacted immediately.

In this study, it was decided that adult patients up to 50 years of age at the time of consent could participate, as neuroplasticity (i.e. ability of the brain to change during life by

Page 34 of 112

Proprietary confidential information © 2023 Boehringer Ingelheim International GmbH or one or more of its affiliated companies

acquiring, storing and re-using information) declines with age as well as with duration of the illness and treatment with antipsychotics.

So far, the acquired clinical data suggest that Iclepertin improves cognition which should translate to functional improvement in day-to-day activities. Therefore patients with functional impairments as described in inclusion criterion #4 will be included in this trial.

This trial is investigating Iclepertin as a treatment for cognitive impairment due to schizophrenia and therefore it is hypothesized that Iclepertin will improve cognitive impairment caused by the disease. Patients who are randomized into the trial must have achieved at least an 8th grade education as a surrogate of pre-morbid cognitive capacity.

Retesting

Retesting applies in situations when the issue can be resolved within the screening period of 35 days, for example patients are testing positive on urine drug screen for cannabis or opioids at Visit 1. These patients can be re-tested once (consider long half-life of cannabis) within the screening period of 35 days, if there is a reasonable explanation and expectation that the patient is not a regular user and will not test positive again on re-test, and at the discretion of the investigator.

In case of retesting, the patient will keep the same patient number. The results of all retests should be available within the 35 days of screening period. Once retests are available and negative for the retested parameter, and in case all other eligibility criteria are met, the patient can be randomized on the planned Visit 2 date.

Rescreening of patients

Rescreening of a patient can be done once, if there is a reasonable explanation and expectation that the patient may have become eligible.

Potential reasons for rescreening could be:

- Hb is too low: Patients with low Hb at screening can be re-screened once the cause of low Hb was successfully treated. The reason and its treatment must be documented in the source documents.
- Active infection with SARS-CoV-2
- Suicidality once the required exclusion period is over
- Clinically significant findings per Investigators judgement
- Stability of Schizophrenia symptoms or medications
- Liver enzyme elevation, e.g., Alanine Aminotransferase (ALT)/ Aspartate Aminotransferase (AST) derangements
- Positive urine drug test at screening visit, if longer wash-out period needed
- Anticholinergic dose exceeding allowed limits, etc.

Background medications should not be adjusted or changed for the purposes of study enrolment or to fulfil eligibility. Changes in background medications should occur per standard of care. Anti-psychotic background therapy must be stable prior to re-screening.

For other potential reasons, please contact the CTL.

Page 35 of 112

Proprietary confidential information © 2023 Boehringer Ingelheim International GmbH or one or more of its affiliated companies

In case of re-screening, the patient will receive a new patient number. The patient and the study partner must sign the current, approved version of the informed consent before any study specific procedures are performed.

- If the patient is re-screened within 12 weeks of the original screening visit, all procedures **except** for the MCCB, SCoRS, VRFCAT and ToL must be performed.
- If the re-screening occurs more than 12 weeks from the initial screening, then all Visit 1 procedures must be repeated.

For all re-screened patients, the screening period will be again 35 days as per protocol. In case all eligibility criteria are met during these repeated screening procedures, the patient can be randomized on the newly planned Visit 2 date under the newly assigned patient number.

3.3.1 Main diagnosis for trial entry

Clinically stable outpatients with established Schizophrenia (as per Diagnostic and Statistical Manual of Mental Disorders, 5th Edition (DSM-5))

Please refer to section 8.3.1 (Source Documents) for the documentation requirements pertaining to the in- and exclusion criteria.

3.3.2 Inclusion criteria

- 1. Patient must be capable of providing a signed and dated written informed consent by visit 1 in accordance with International Council on Harmonisation for Good Clinical Practice (ICH-GCP) and local legislation prior to admission to the trial.
- 2. Male or female patients who are 18-50 years (inclusive) of age at time of consent.
- 3. Diagnosis of schizophrenia utilizing DSM-5 with the following clinical features:
 - Outpatient, clinically stable and in the residual (non-acute) phase of their illness.
 - No hospitalization¹ or increase in level of psychiatric care² due to worsening of schizophrenia within 12 weeks prior to randomization.
 - score: items P1, P3-P6 \leq 5 and item P2 and P7 \leq 4 at Visit 1, and confirmed at Visit 2.
- 4. Patients should have functional impairment in day-to-day activities such as difficulties following conversation or expressing themselves, difficulties staying focused, difficulties remembering instructions, what to say or how to get to places, per investigator judgement.
- 5. Patients maintained on current antipsychotic treatment (minimum 1 and maximum 2 antipsychotics, but clozapine is not allowed) for at least 12 weeks and on current dose for at least 35 days prior to randomization.

This includes home hospitalization for exacerbation in countries where it applies, however **NOT** hospitalization for social management and/or day programs.

² This includes home hospitalization, partial hospitalization or ER visits.

Page 36 of 112

Proprietary confidential information © 2023 Boehringer Ingelheim International GmbH or one or more of its affiliated companies

- For patients on two antipsychotics, at least one antipsychotic must be within the approved label dose range. The second antipsychotic must not exceed the maximum daily dose per local label. **Note:** If the total dose is stable, different dosage forms of the same antipsychotic treatment will be considered as one antipsychotic.
- 6. Patients with any other concomitant psychoactive medications (except for anticholinergics) need to be maintained on same drug for at least 12 weeks and on current dose/regimen for at least 35 days prior to randomization.
 - Maximum daily benzodiazepine load of up to 1 mg lorazepam-equivalent as needed (pro re nata, prn). Table of relevant medications and their equivalencies will be provided as a part of ISF
 - For any other psychoactive medications cannot exceed the maximum daily dose per local label of the country where the study is being conducted.
- 7. Women of childbearing potential (WOCBP)¹ must be ready and able to use highly effective methods of birth control per Non-Clinical Safety Studies for the Conduct of Human Clinical Trials and Marketing Authorization for Pharmaceuticals (ICH M3 (R2)) that result in a low failure rate of less than 1% per year when used consistently and correctly. A list of contraception methods meeting these criteria is provided in Section 4.2.2.3. Such methods should be used throughout the trial, and for a period of at least 35 days after last trial drug intake, and the patient must agree to periodic pregnancy testing during participation in the trial.
- 8. Have a study partner, defined as any person either private or professional who knows the patient well, has been capable of interacting with the patient on regular basis, and preferably consistent throughout the study.
 - The study partner must interact with the patient at a minimum one hour per week and, preferably, at least 2 times a week. At least one interaction per week should be in person.
 - The study partner must have educational achievement of minimum 8th grade.
 - Professional study partners (e.g. study nurse, social worker etc.) are allowed if not involved in administration of any of the protocol assessments.
- 9. Patients must, in the investigator's opinion, exhibit reliability and physiologic capability (e.g. sufficient hearing, vision etc.), to comply with all protocol procedures, and have attained an educational achievement of minimum 8th grade.
- 10. Patients and his/ her study partner must be fluent in the language of the batteries/ questionnaires.

_

¹ A woman is considered of childbearing potential (WOCBP), i.e. fertile, following menarche and until becoming postmenopausal unless permanently sterile. Permanent sterilisation methods include hysterectomy, bilateral salpingectomy and bilateral oophorectomy. Tubal ligation is NOT a method of permanent sterilisation. A postmenopausal state is defined as no menses for 12 months without an alternative medical cause.

3087946-03 Clinical Trial Protocol Page 37 of 112

Proprietary confidential information © 2023 Boehringer Ingelheim International GmbH or one or more of its affiliated companies

3.3.3 Exclusion criteria

- 1. Patient with current DSM-5 diagnosis other than Schizophrenia, including but not limited to bipolar, schizoaffective, major depressive disorder etc. The Mini-International Neuropsychiatric Interview (M.I.N.I.) for psychotic disorders should be used for guidance.
- 2. Cognitive impairment due to developmental, neurological (e.g., stroke) or other disorders including head trauma, or patients with dementia or epilepsy.
- 3. Severe movement disorders
 - Leading to cognitive impairment (e.g. Parkinson's dementia), or
 - Interfering with the efficacy assessments, or
 - Due to antipsychotic treatment that cannot be controlled with low dose anticholinergic treatment (equal to maximum 1 mg benztropine twice daily). Table of relevant medications and their equivalencies will be provided as a part of ISF
- 4. Any suicidal behavior in the past 1-year prior to screening and during the screening period.
- 5. Suicidal ideation of type 5 in the C-SSRS (i.e. active suicidal thought with plan and intent) in the past 3 months prior to screening and up to and including Visit 2.
 - Patients with Suicidal Ideation type 4 in the C-SSRS (i.e. active suicidal thought with intent but without specific plan), within 3 months prior to screening and up to and including visit 2, can be randomized in the study, if assessed and documented by a licensed mental health professional that there is no immediate risk of suicide.
- 6. History of moderate or severe substance use disorder (other than caffeine and nicotine), as defined in DSM-5 within the last 12 months prior to informed consent.
- 7. Positive urine drug screen at Visit 1 based on central lab test. For a list of drugs assessed in the urine drug screen, please refer to Table 5.2.3:1.
- 8. Patients who were treated with any of the following within 6 months prior to randomization:
 - Clozapine
 - Stimulants (e.g. methylphenidate, dextroamphetamine, modafinil)
 - Ketamine or esketamine
 - Electroconvulsive therapy (ECT) or modified ECT
- 9. Participation in any investigational psychoactive drug trial (both industry/ academic) in last 6 months, and 30 days or 5 half-lives for no-psychoactive drug trial, prior to randomization.
- 10. Patients who were previously treated with Iclepertin.
- 11. Patients who are treated with any of the following within the last 35 days prior to randomization¹:
 - Strong or moderate CYP3A4 inhibitors including grapefruit juice

¹ List of relevant medications will be provided as part of the ISF

- Strong or moderate CYP3A4 inducers including St. John's wort (Hypericum perforatum)
- Dietary supplements and herbal remedies that may impact cognition, in the investigator's judgement
- Antiepileptics (when used for the treatment of epilepsy)¹
- Tricyclic antidepressants
- Traditional Chinese medicine/ non-Western therapy
- Medical devices therapy (e.g. TMS, neurofeedback)
- 12. Patients who plan to change their current life-style habits including but not limited to alcohol, nicotine or caffeine use, or diet, during the treatment period.
- 13. Patients who have participated in a clinical trial with repeated assessments (i.e. a single assessment is not exclusionary) with the MCCB and/ or any other schizophrenia cognitive battery within 12 weeks prior to screening.
- 14. Any formal Cognitive Remediation Therapy (CRT) within 12 weeks prior to screening. Initiation of CRT is not allowed during the study.
- 15. Initiation or change in any type or frequency of psychotherapy (e.g. cognitive behavioral therapy, social skills training, vocational/occupational therapy) within 12 weeks prior to randomization. Patients with ongoing, stable psychotherapy for more than 12 weeks prior to randomization (and intend to maintain the same frequency during the study) may qualify as per clinical judgement of the investigator.
- 16. Any of the following, in the judgment of the investigator:
 - Clinically significant finding of the physical examination, vital signs (including blood pressure (BP) and pulse rate (PR)), ECG or laboratory value (as measured by the central laboratory) that would jeopardize the patient's safety while participating in the trial or their capability to participate in the trial.
 - Symptomatic/unstable/uncontrolled or clinically relevant concomitant disease or any other clinical condition that would jeopardize the patient's safety while participating in the trial or capability to participate in the trial.
 - Significant or unstable physical condition that may require change in medication or hospitalization that would impact cognitive function.
 - Planned major surgery requiring withdrawal from study medication for more than 2 weeks during the study period.
 - Note: Please contact sponsor in case of you have any questions.
- 17. Hb below lower limit of normal at Visit 1 assessed by the central lab.
- 18. History of haemolytic anaemia including hemoglobinopathies (for example thalassemia or sickle-cell anaemia), RBC membrane diseases or known G6PDH (Glucose-6phosphate dehydrogenase) deficiency; or current anaemia or patients planning to donate blood.

Antiepileptics as monotherapy when used for other indications are acceptable if they fulfil criteria detailed in inclusion criteria #6, and should not be started during the treatment period if at all possible.

Page 39 of 112

Proprietary confidential information © 2023 Boehringer Ingelheim International GmbH or one or more of its affiliated companies

- 19. Severe renal impairment defined as an eGFR < 30mL/min/1.73m² assessed by the central lab at Visit 1.
- 20. Indication of liver disease, defined by serum levels of either ALT (SGPT), AST (SGOT), or alkaline phosphatase above 3 times upper limit of normal (ULN) assessed by the central lab at Visit 1.
- 21. Known history of HIV and/ or known on-going Hepatitis B or C infections.
- 22. Patients with known active infection with SARS-CoV-2 within the last 35 days prior to randomization.¹
- 23. Any documented active or suspected malignancy or history of malignancy within 5 years prior to screening, except appropriately treated basal cell carcinoma of the skin, squamous cell carcinoma of the skin or in situ carcinoma of uterine cervix.
- 24. Women who are pregnant, nursing, or who plan to become pregnant while in the trial.
- 25. Patient who did not complete the MCCB at Visit 1 and therefore does not have T score for randomization.
- 26. Patients with an allergy to Iclepertin and/or any of the excipients (including lactose). A list of Iclepertin and placebo ingredients are provided in the Investigators' Brochure.

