Moderate or strong CYP3A4 inhibitors CYP3A4 sensitive drugs with narrow therapeutic index (NTI)	Exposure of Iclepertin will increase in the presence of the moderate or strong CYP3A4 inhibitors Exposure of CYP3A4 sensitive drugs with NTI decreases during treatment with Iclepertin	Patients should not be randomized if taking any of the drugs listed in the ISF or need such drug during treatment period (refer section 4.2.21). Patients requiring Paxlovid (a strong CYP3A inhibitor) for the treatment of COVID-19 during the trial should stop taking Iclepertin at time point of Paxlovid start, and restart Iclepertin 1 day after Paxlovid cessation.
Disease Related Risk		
Worsening of Schizophrenia or relapse	Clinically stable patients with schizophrenia are randomized to this study. Schizophrenia is a cycling disease with fluctuation of symptom severity: acute episodes (e.g., relapse) and intervals of relative stability (e.g., remission) between them.	Monitoring of symptoms of schizophrenia with adjustment of maintenance standard of care (SoC) treatment to control symptoms. Definition of relapse provided to monitor in a standardized manner.

Page 24 of 112

Proprietary confidential information © 2023 Boehringer Ingelheim International GmbH or one or more of its affiliated companies

Table 1.4.2:1 Overview over trial related risks (con't)

Possible or known risks of clinical relevance for this trial	Summary of data, rationale for the risk	Mitigation strategy
Disease Related Ri	sk	
Potential worsening of existing or new side effects caused by treatment with antipsychotics (e.g. tardive dyskinesia, metabolic, orthostatic hypotension)	No worsening of the AEs due to antipsychotic treatment were seen in the phase II study.	AE monitoring Extrapyramidal symptoms (EPS) assessed using Simpson Angus Scale (SAS)/ Abnormal Involuntary Movement Scale (AIMS)/ Barnes Akathisia Rating Scale (BARS) throughout treatment period Per investigator judgement adjustment of background medication is allowed.

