4.2.2 Restrictions

4.2.2.1 Restrictions regarding concomitant treatment

Medications and non-pharmacological interventions that are exclusionary under the eligibility criteria (Section 3.3.3) are restricted during the treatment period as well.

In addition, the following concomitant medication and treatment restrictions apply for the duration of the treatment period:

- Medications that are NOT allowed 8 hours prior to MCCB assessment performed at visit 2, visit 6, EOT/Visit 11 and eEOT (if applicable).
 - o Antihistamines with prominent sedative side effects,
 - Anticholinergics
 - o Benzodiazepines

BI Trial No.: 1346-0012 c33087946-03

3087946-03 Clinical Trial Protocol Page 47 of 112

Proprietary confidential information © 2023 Boehringer Ingelheim International GmbH or one or more of its affiliated companies

- o Other sedative medications
- o Short term use of opioids for pain, cough or diarrhea

Anticholinergics

- The total daily dose must not exceed 1 mg benztropine twice daily or equivalence.
- o If patient's are being treated with more than 1 anticholinergic (including OTCs), the total daily dose still must not exceed 1 mg benztropine twice daily equivalence (e.g., diphenhydramine is an antihistamine with anticholinergic component).
- O Patients should remain on stable anticholinergic dose, unless absolutely necessary to adjust for medical reasons.
- Screening period can be used to reduce anticholinergic use to maximum 1 mg benztropine twice daily in total, if clinical situation allows per investigator's judgement.

• Antihistamines

- Patients taking sedative antihistaminic medication should be on a stable dose not exceeding daily recommended dose per label in the country.
- Opioid maintenance therapy or opioid-replacement for opioid dependence (e.g. methadone) is not allowed during the trial period.
- CYP3A4 sensitive drugs with NTI (e.g., fentanyl, cyclosporine) are not allowed during treatment with Iclepertin. List is included in the ISF.

Permitted therapies include:

- Non-systemic use (topical, inhalation or nasal administration) of antihistaminics and anticholinergies is allowed.
- Short-term opioid therapy up to 4 weeks per time, for example with cough syrup or pain killer, is allowed (except fentanyl).

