Temporary treatment discontinuation or interruption due to other reasons	Identified from data collected in the Temporary Discontinuation page of the CRF.	Hypothetical – only data collected from the end of REP after the interruption, to end of the interruption will be subject to exclusion from the analysis
Temporary treatment-switch	Identified from the dispensation records. Temporary treatment-switch will be handled as temporary interruptions in the same way for	Hypothetical – only data collected from the end of REP after the treatment switch, to end of the

due to dispensation error	both directions (iclepertin to placebo or placebo to iclepertin)	treatment switch will be subject to exclusion from the analysis			
Early Perman	Early Permanent Treatment Discontinuation				
Exacerbation or acute episode of schizophrenia resulting in early termination of treatment	Identified from data collected in the Adverse Event page of the CRF:  - "Drug Withdrawn" reported in the Action Taken with Study Treatment field, and  - Category reported as "Schizophrenia Relapse" or MedDRA preferred term coded as	Treatment policy			
Investigator assessed drug- related adverse events which lead to early termination	"Schizophrenia"  Identified from data collected in the Adverse Event page of the CRF:  - "Drug Withdrawn" reported in the Action Taken with Study Treatment field, and	Treatment policy			
of study medication	- "Yes" reported in the Relationship to Study Treatment field				
Protocol-defined drug withdrawal due to treatment – haemoglobin decrease	Identified from data collected in the End of Treatment and Adverse Event pages of the CRF and laboratory data:  - Subject who did not complete the planned treatment period as reported in the End of Treatment page with reason being "Adverse Event", and  - AE indicating haemoglobin decrease with action taken being "Drug Withdrawn"	Treatment policy			
Protocol-defined drug withdrawal due to treatment – CYP3A4 inhibitors or CYP3A4 sensitive drugs with NTI	Identified from data collected in the End of Treatment page of the CRF:  - Subject who did not complete the planned treatment period as reported in the End of Treatment page with "Protocol Deviation" as the reason, and  - Use of CYP3A4 inhibitors or CYP3A4 sensitive drugs with	Treatment policy			

	NTI specified as the detailed reason of discontinuation	
Early termination of study	Identified from data collected in the End of Treatment page of the CRF:	Hypothetical

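### The risk table keeps patients on narrow-therapeutic-index CYP3A4 substrates out of randomisation, but no eligibility criterion names the class, so the eligibility check does not enforce this

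*Protocol*

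**What the plan says.** - **Protocol Section 1.4.2, Table 1.4.2:1 (drug interactions).** Two classes stand together: moderate or strong CYP3A4 inhibitors, which raise iclepertin exposure, and CYP3A4-sensitive NTI drugs. For the second class the stated risk is "Exposure of CYP3A4 sensitive drugs with NTI decreases during treatment with Iclepertin". The mitigation reads "Patients should not be randomized if taking any of the drugs listed in the ISF or need such drug during treatment period". It refers to a section printed as 4.2.21, evidently Section 4.2.2.1.
- **Protocol Section 3.3.3, exclusion 11.** The lead-in is "Patients who are treated with any of the following within the last 35 days prior to randomization". The CYP3A4 items under it are "Strong or moderate CYP3A4 inhibitors including grapefruit juice" and "Strong or moderate CYP3A4 inducers including St. John's wort". The other items are supplements and herbal remedies, antiepileptics used for epilepsy, tricyclics, traditional Chinese or non-Western therapy, and device therapy. A footnote adds "List of relevant medications will be provided as part of the ISF".
- **Protocol Section 4.2.2.1.** Whatever is exclusionary under Section 3.3.3 is also restricted during treatment. A second, additional set of restrictions then covers the treatment period, and it includes "CYP3A4 sensitive drugs with NTI (e.g., fentanyl, cyclosporine) are not allowed during treatment with Iclepertin", with a list in the Investigator Site File (ISF).
- **SAP Section 6.3, Table 6.3: 1.** One treatment-policy row covers early permanent discontinuation with "Use of CYP3A4 inhibitors or CYP3A4 sensitive drugs with" NTI given as the detailed reason.

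**The concern.** The sponsor identified lower exposure to NTI drugs as a clinically relevant risk and chose non-randomisation as the mitigation. That works only if the class is in the list that sites check before randomising, and it is not. Section 4.2.2.1 places NTI drugs among the restrictions that come on top of the exclusionary ones, which implies that they are not exclusionary. The risk table implies that they are.

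The first stake is safety: a patient whom the risk table meant to keep out can receive the first dose while taking the interacting drug. The second is conduct: the site has followed the criteria correctly and still has a conflict with the protocol on Day 1. A possible third is analysis, because such a patient belongs to the Randomized Set and any later stop is handled as an intercurrent event.

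**Working it through.** No arithmetic applies. The check sets the passages side by side.

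**Step 1. Where each class appears.**

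| Class | Table 1.4.2:1 (do not randomise) | Inclusion/exclusion criteria | Section 4.2.2.1 (during treatment) |
|---|---|---|---|
| Moderate/strong CYP3A4 inhibitors | yes | yes, exclusion 11 | yes, carried over from 3.3.3 |
| CYP3A4-sensitive NTI drugs | yes | no, absent from all 10 inclusion and 26 exclusion criteria | yes, as an additional restriction |

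The synopsis criteria do not name the NTI class either.

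**Step 2. Whether another criterion catches it.** The footnote to exclusion 11 points to a list of drugs for the classes which that criterion names; on its face it adds no class. Exclusion 16 allows investigator judgement on clinical findings, concomitant disease and physical condition, but names no interacting drug. Section 4.2.2.1 carries the exclusions forward into treatment; nothing carries its additional restrictions back into eligibility.

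**Step 3. What governs randomisation.** Section 4.1.3 randomises after assessment of the inclusion and exclusion criteria. Section 6.2.2 has screening data reviewed against the eligibility criteria. Section 8.3.1 requires source evidence on those criteria before allocation. Section 3.3 defines randomisation in error by the same criteria. None of these refers to Table 1.4.2:1.

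**Step 4. The path of one patient.** A patient stably taking an NTI substrate meets no numbered exclusion on that ground, so can be randomised at Visit 2 and is not randomised in error under Section 3.3. The first dose is taken at the end of Visit 2 (Section 4.1.4). From that dose the patient is in conflict with Section 4.2.2.1. The rule in Protocol Section 7.2.1 and SAP Section 6.4 that removes patients from the Randomized Set does not apply: it requires both randomisation in error and discontinuation before trial medication starts.

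**Step 5. What the analysis then does.** This depends on later events:

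- Trial drug continues: no treatment-discontinuation event arises, and the MCCB data are used.
- Trial drug is interrupted for this reason: SAP Table 6.3: 1 applies the hypothetical strategy. Data from the end of the 12-day residual effect period until the interruption ends are excluded.
- Trial drug is stopped permanently, the End of Treatment reason is protocol deviation, and NTI or inhibitor use is the detailed reason: treatment policy applies, and later data are kept.
- Trial drug is stopped permanently under another recorded reason, with no other treatment-policy event: the hypothetical strategy applies. Data beyond the last dose plus 12 days are excluded.

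The documents give no basis for estimating how often any of these paths would occur.

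**The case against.** **The protocol already forbids the combination.** The risk table says not to randomise, and Section 4.2.2.1 bars the drugs from the first dose. This stands. A reader might infer that the protocol permits these patients to be treated; read as a whole it does not. What remains is that the criteria sites must document do not carry the prohibition.

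**The randomisation sentence might belong to inhibitors only.** The worked example after it, Paxlovid, is an inhibitor. If the table layout ties the sentence to that class alone, the risk table and the criteria agree. Against this, both classes and both risks come before the one mitigation text, and its cross-reference leads to the section holding the NTI restriction and its ISF list. The shared reading is the more natural, but it is a reading. Even on the narrower one, Step 4 holds: the patient passes the criteria and conflicts with Section 4.2.2.1 at the first dose.

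**The ISF lists may close the gap in practice.** They are not part of the documents, so this cannot be excluded. It would still leave the protocol inconsistent.

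**Placing NTI drugs under treatment restrictions may be deliberate.** The stated risk is one of concurrent use, and Table 1.4.2:1 gives no look-back. This stands against one tempting remedy, adding the class to exclusion 11, because that would import a 35-day window which the risk table does not state.

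**Conclusion.** The inconsistency is real. Table 1.4.2:1 and Section 3.3.3 disagree on whether use of an NTI substrate at entry bars randomisation, and the eligibility check follows Section 3.3.3. The conclusion rests on the mitigation text covering both classes and on the ISF lists not adding an entry criterion.

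Its size is limited. The number of patients is not stated. It is probably small, given stable outpatients aged 18 to 50 and the examples named (fentanyl, cyclosporine), but that is a judgement, not a figure from the documents.

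Two stronger readings are not supported:

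- *Trial treatment must stop in every such patient.* Protocol Section 3.3.4.2 ties withdrawal to restricted medication that may affect safety, leaves it to the investigator's clinical judgement, and asks for consultation with the sponsor. Section 3.3.4.1 also allows temporary discontinuation.
- *The primary comparison is diluted by near-untreated patients.* Step 5 shows that later data stay in under the NTI row only with a specific recorded reason, and near-untreated data would require a very early stop. Treatment policy for these withdrawals is a stated choice in Protocol Section 7 and applies equally to NTI drugs started mid-trial. No material effect on the estimate or on power is shown.

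The point is therefore a safety-relevant inconsistency that should be corrected, not a threat to the primary analysis.

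**What to change.** Reconcile Protocol Table 1.4.2:1, Section 3.3.3 and Section 4.2.2.1 on one question: does use of a CYP3A4-sensitive NTI drug at entry bar randomisation? State the answer in the same terms in all three places, and use the agreed list in the eligibility check at Visits 1 and 2. Correct the cross-reference printed as 4.2.21 at the same time. The sponsor's clinical team decides which rule holds and whether any look-back period applies; this review takes no position on either.

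The cost is about one line in a protocol amendment, plus alignment of site materials. Section 4.2.2.1 states that an NTI list is included in the ISF, so no new list should be needed. If the decision is that use at entry bars randomisation, expect some extra screen failures, probably few. If it is that it does not, the wording of Table 1.4.2:1 has to change, and Section 4.2.2.1 has to be consistent with it from the first dose. No change to the SAP is required on this account.
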